19.3.3. Additional Data Collection

Heart failure clinical outcomes will be assessed. The measurements, including NYHA classification, death, heart failure related hospitalization, heart failure related study exits and subject self-reported global assessment for each subject will be obtained at 6 months post-implant. Summary statistics will be provided.

19.3.3. Overall Study Sample Size Requirements

The sample size requirement at 6-months for each of the study objectives is displayed in Table 18. The first row does not account for attrition, while the second row is inflated by 15% attrition. The sample size for Secondary Objective #2 assumes the conservative case that the interim look results in, no borrowing of historical data. Therefore, the overall sample size for the study is 471.

Table 18: Required Sample Size by Study Objective

	Primary Safety Objective	Primary Efficacy Objective #1	Primary Efficacy Objective #2	Secondary Objective #1	Secondary Objective #2 (post-implant failure modes)	Secondary Objective #3	Overall
Number needed at 6-months	170	145	50	NA	400	NA	400
Number of enrollments	200	171	59	NA	471	NA	471

20. Ethics

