Up to 471 subjects will be enrolled into the study and up to 471 Attain Stability Quad MRI SureScan LV Lead (Model 4798) implanted, to ensure a minimum effective sample size of 400 Model 4798 leads implanted with 6 months post implant follow up visits (assuming 15% attrition). For the secondary endpoint of individual lead failure modes, Bayesian methods utilizing data from up to 37 historical patients will be used. All other objectives will be analyzed using only patients enrolled in this study. After a successful implant, threshold testing will occur to show one LV vector with pacing capture threshold (PCT) ≤ 2.5 [contact] and with sufficient safety margin was programmed. Subjects will then be followed at implant, three months, six months and every six months thereafter until FDA approval is obtained or until study closure, whichever comes first.

See Figure 1 and Section 15 for further detail on study procedures and data collection as well as time-points for data collection.

Figure 1: Study Visits

The study is expected to be conducted at up to 56 sites worldwide. Participating geographies are expected to include, but are not limited to: the United States, Canada, EMEA, Malaysia, and Hong Kong. To ensure a widespread distribution of data and to minimize site bias in the study results, the maximum number of subjects allowed at a single site is 50 subjects.

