12.1. Duration

The study duration is expected to be approximately 19 months. This represents 13 months for subject enrollment and 6 months for subject follow-up for the last subject enrolled. Subjects are anticipated to be in the study for on average 12 months. The first enrollment is projected to occur in May 2017. Subjects will complete visits at enrollment/baseline, implant, 3 months, 6 months, and then every 6 months thereafter. Subjects will not be replaced with newly enrolled subjects upon early exit. As described in Section 19, the sample size accounts for attrition.

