18.2. Data Monitoring Committee

A Data Monitoring Committee (DMC) will not be utilized for this study considering:

- An independent CEC will be formed to adjudicate at minimum all system and procedure related events and all deaths.
- This study does not meet FDA's recommended criteria (Guidance for Clinical Trial Sponsors: Establishment and Operation of Clinical Trial Data Monitoring Committees) for when a study should use a DMC, primarily because the study is not evaluating the effectiveness of a treatment intended to prolong life or reduce the risk of a major adverse health outcome.
- As a result of risk analysis and mitigation efforts as outlined in Section 16, any residual risk associated with this study is considered low and acceptable.
- The Attain Stability Quad MRI SureScan LV Lead (Model 4798) is a modification of the currently market approved Attain Performa lead Models 4298, 4398, and 4598 is a modification of the currently market approved Model 4396 LV lead. The Attain Stability Quad lead Model 4798 has a similar electrode spacing as the Attain Performa lead Models 4298, 4398, and 4598.
- Study will be conducted under FDA oversight via an investigational device exemption (IDE).

19. Statistical Design and Methods

This section presents statistical considerations for the study design and provides a high-level description of planned analysis and reporting. More details will be given in a separate Statistical Analysis Plan (SAP) that will be completed before data freeze for the primary objective analysis. Any deviation to the pre-specified statistical analyses will be noted in the study report. The analysis of the study objectives will be completed when the sample size requirements (see Table 18) for all the study primary and secondary objectives are met. An interim analysis will be conducted when 360 subjects are enrolled in the study. This interim analysis is specifically designed for one of the secondary objectives (details in Section 19.2.2).

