Figure 8 illustrates the effect of the power prior coupled with the loss function. The figure shows credible intervals in scenarios where the prior is optimistic (better performance than current study), in agreement (similar performance to the current study), and pessimistic (worse performance than the clinical study). Note that the prior data source in Figure 8 is the Attain Performa study, with 401 patients. As will be discussed later, these data are scaled to represent a maximum of 37 patients (i.e. 9% weight).

Figure 8: Credible Intervals for Scenarios of Agreement Between Historical and Current Data

The prior data set in Figure 8 has 401 samples. However, the maximum effective historical data sample size is $n_h = 37$, for a maximum weight of 9%. Therefore, the prior will be scaled by a factor of $(37/401)$. As an example, illustrated in the middle panel above, if the effective sample size is 34 out of 37, the prior has received 89% of the maximum weight, or 8.5%.

The panels in Figure 8 can be interpreted as follows:

- **Top panel:** The current data shows lower performance than the prior. The loss function produces a substantial penalty resulting in almost no weight to the prior (1%). The posterior (final estimate) is essentially the same as the current study.
- **Middle panel:** The current data is very similar to the prior. The loss function penalty is small, resulting in a prior weight of 8.5% (recall that the maximum weight is 9.2%). Because the agreement is good, the posterior (final estimate) is similar to both the prior and current study.
- **Bottom panel:** The current data is very similar, with slightly better performance than the prior. The loss function produces a weight very close to the maximum of 9.2%. The posterior (final estimate) is a balance between the prior and current study.

Sample Size

A Bayesian adaptive design is set up to enroll patients until a sufficient sample size is achieved to have high probability of meeting the required effective sample size of $n_e = 400$. The number of enrolled patients in the study may vary from 363 to 400 subjects due to the adaptations to the trial. This study follows methods from Berry, et.al.²⁷

The interim analysis will take place after 360 subjects have been enrolled into the study.

The Adaptive Bayesian sample size algorithm will stop or continue enrollment accordingly to the following:

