- 1.) If the predictive probability of $n_e \geq 400$ is larger than 80% then enrollment will stop.
- 2.) If the predictive probability of $n_e \geq 400$ is less than 80%, enroll sufficient additional patients to make the probability of $n_e \geq 400$ at least 80%.

At the time of the interim analysis, some patients will not have completed the full evaluation period. A longitudinal model will be employed to enable final observations to be imputed for those subjects with incomplete information.

There are 3 types of subjects at a given interim analysis:

- 1.) Subjects that have complete data
- 2.) Subjects that have partial data (censored value at a particular time)
- 3.) Subjects that have no information (subjects that have not been enrolled)

Predictive probabilities for types 2 and 3 will have to be computed. The predictive probability model that will be used is a piecewise exponential. This will allow the final outcomes for the subjects who have not had an event and have not completed 6 month follow up to be simulated.

Note this Bayesian approach to borrow information from historical datasets will only be used for the secondary objective #2.

19.2.3. Secondary Objective # 3

Objective – Electrical measurements (PCT and Impedance) at follow-ups

Pacing Capture Threshold (PCT) and impedance data will be collected using VectorExpress™. Pacing vector changes will be monitored for all implanted patients at follow-up visits.

Summary statistics for PCT and impedance at each time point (i.e. Implant, 6 months, etc.). The distribution of the electrical measurements at the final programmed pacing vector will be presented as n, mean, standard deviation, minimum, median and maximum. In the event of a replacement of a Medtronic Quad CRT-P or CRT-D device and/or the implanted LV lead, only measurements from the

Attain Stability Quad MRI SureScan LV Lead (Model 4798) implanted at the initial implant procedure will be included in the analysis cohort for this objective.

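### Section 19 ties the analysis of every objective to 400 subjects at 6 months for a descriptive secondary objective, but the capped enrolment of 471 makes 400 only the expected number

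*Protocol*

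**What the plan says.** The protocol file carries two versions; the text on this point is the same in both.

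- **Target and enrolment (section 19.3.3, Table 18).** Secondary objective #2 needs 400 subjects at 6 months. On the two rows of the table: "The first row does not account for attrition, while the second row is inflated by 15% attrition". The entry for this objective "assumes the conservative case that the interim look results in, no borrowing of historical data". Enrolment is then fixed: "Therefore, the overall sample size for the study is 471".
- **Cap and purpose (synopsis and section 12).** Enrolment may go up to 471, at an assumed 15% attrition, "to ensure a minimum effective sample size of 400 Model 4798 leads implanted with 6 months post implant follow up visits".
- **No replacement (section 12.1).** "Subjects will not be replaced with newly enrolled subjects upon early exit".
- **Interim rule (section 19.2.2).** After 360 enrolments, if the predictive probability that the effective sample size reaches 400 is below 80%, the sponsor is to "enroll sufficient additional patients to make the probability of" reaching 400 at least 80%. No cap is named there. The same section gives 363 to 400 as the range for the number enrolled.
- **Trigger (opening of section 19).** One condition covers every objective; their analysis "will be completed when the sample size requirements (see Table 18) for all the study primary and secondary objectives are met".
- **Status of the objective (section 11.1.2).** The secondary objectives are descriptive and carry no performance requirement. The primary rows of Table 18 are 170, 145 and 50.

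**The concern.** Dividing by the retention rate sets the expected number of completers equal to the target. It does not make reaching the target likely. The synopsis and section 12 nevertheless present 471 as securing 400, and section 19.2.2 sets an 80% standard for the same target.

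This matters because of the trigger. If the effective number falls just short of 400, the written condition for analysing any objective, including primary safety and efficacy, is not met. The cap and the no-replacement rule leave no way within the plan to meet it, and no fallback is given. The sponsor would have to exceed the cap or choose an analysis time outside the plan, in a study with no control group (section 14.1) and no data monitoring committee (section 18.2). Low borrowing arises when the new lead looks worse than the historical data, which is when an unplanned choice of timing is least welcome.

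**Working it through.** **Inputs.** Target 400, attrition 15%, no borrowing and 471 enrolled (section 19.3.3); 80% assurance, at most 37 borrowed subjects and the weight function (section 19.2.2). Assumptions: subjects drop out independently at the planned rate, and borrowed subjects count towards the 400, which is the reading favourable to the plan.

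**1. Reproduce the plan's figure.** 400 / 0.85 = 470.6, rounded up to 471. The same formula gives the other enrolment entries in Table 18: 170 / 0.85 = 200, 145 / 0.85 = 170.6 → 171, and 50 / 0.85 = 58.8 → 59. The plan's arithmetic is correct.

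**2. What 471 delivers with no borrowing.** Let X be the number with 6-month data, X ~ Binomial(471, 0.85).
- Mean: 471 × 0.85 = 400.35.
- P(X ≥ 400) = 0.550, so a 45% chance of fewer than 400.

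**3. Enrolment needed for 80% with no borrowing.** P(X ≥ 400) is 0.779 at N = 477 and 0.809 at N = 478. The answer is 478, which is 7 above the cap (7 / 471 = 1.5%).

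**4. Dependence on attrition (N = 471, no borrowing).**

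| Attrition | P(X ≥ 400) |
|---|---|
| 13% | 0.918 |
| 13.8% | 0.809 |
| 14% | 0.772 |
| 15% | 0.550 |
| 16% | 0.318 |
| 17% | 0.146 |

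**5. Dependence on borrowing (N = 471, 15% attrition).** With b borrowed subjects the requirement becomes X ≥ 400 − b.
- b = 5: P(X ≥ 395) = 0.777.
- b = 6: P(X ≥ 394) = 0.813.

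For either historical source the borrowed number is at most 37 × [1 − exp(−(5p)²)], where p is the plan's posterior probability that the current complication rate is no higher than the historical one. Setting this to 6 gives exp(−25p²) = 1 − 6/37 = 0.838, so p is about 0.084.

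| p | Borrowed | P(reaching 400) |
|---|---|---|
| 0.10 | 37 × 0.221 ≈ 8 | 87% |
| 0.20 | 37 × 0.632 ≈ 23 | 99.8% |
| 0.50 | 37 × 0.998 ≈ 37 | above 99.99% |

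**6. The primary rows.** The largest is 170. With 471 enrolled and 85% retained, the probability of at least 170 is 1 to many decimal places. The primaries' own requirements are not at risk.

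**The case against.** **The binomial may not be the probability in the 80% rule.** Section 19.2.2 describes a predictive probability over pending complication outcomes and the resulting borrowing, using a piecewise exponential model. No dropout model is given. The 363 to 400 range equals 400 − 37 up to 400, which fits a rule that counts subjects before any attrition allowance, with attrition added afterwards in Table 18. On that reading the two sections are successive layers. This stands in part. A reader might infer that 471 flatly contradicts the 80% rule, but the documents do not define the rule closely enough to support that. Still, section 19.2.2 calls these subjects enrolled, the same term used for the 471, so the figures need reconciling. The trigger problem in section 19 does not depend on which reading is right.

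**Zero borrowing is a corner case, and the gap is seven subjects.** This stands. A reader might carry the near-even chance over to low borrowing in general, but step 5 shows otherwise: 80% is restored once p passes about 0.085. Section 19.1.1 expects performance similar to Model 4298, and better performance also earns full weight.

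**Inflating by expected attrition is ordinary practice, and the assurance is qualified by the 15% assumption.** This stands as far as the calculation goes: 471 is not a miscalculation. It does not rescue the promise of a minimum, because the 55% is computed at that same 15%.

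**The natural cut-off is the last subject's 6-month visit, and the SAP may say so.** That is the sensible cut-off, but it is not what section 19 says. The cap, the no-replacement rule and the trigger are all fixed in the protocol.

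**Conclusion.** Wrong as written, with a small practical size. Section 19 makes the primary analyses wait for a descriptive secondary target that capped enrolment reaches with only about 55% probability in the case used to derive the cap, against the 80% asked for in section 19.2.2. No fallback is stated. The 55% rests on 15% attrition, independent subjects and no borrowing. It rises above 80% with about 6 effective borrowed subjects or with attrition of about 13.8% or less, and it falls quickly if attrition exceeds plan.

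Two stronger conclusions might be inferred, and neither is supported. The primary objectives are not short of subjects: 170, 145 and 50 are met with near certainty, so the effect is on the timing and authority of the analysis, not on power. Nor does the study need more patients: 478 only measures the gap between the cap and the 80% standard.

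**What to change.** Wording changes only:

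1. **Section 19, trigger.** *The primary analyses are performed when every enrolled subject has completed the 6-month visit or exited, provided the primary-objective rows of Table 18 (170, 145 and 50) are met. Secondary objective #2 is reported with the effective sample size achieved.*
2. **Section 19.2.2.** State that the 80% rule applies up to the cap of 471. Reconcile the 363 to 400 range with 471 by saying whether it counts subjects before or after attrition.
3. **Synopsis, section 12 and section 19.3.3.** Replace the promise of a minimum with the true property: *471 gives an expected 400 subjects with 6-month data at 15% attrition (about a 55% chance of at least 400 if nothing is borrowed).*

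The cost is a protocol wording amendment and a less favourable statement of assurance. No patients are added.

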20.1. Statement(s) of Compliance

This study will be conducted in compliance with international ethical and scientific quality standards, known as good clinical practice (GCP). Good Clinical Practice includes review and approval by an independent IRB/EC before initiating a study, continuing review of an ongoing study by an IRB/EC, and obtaining and documenting the freely given IC of a subject before initiating the study.

The clinical investigation shall not begin until all required approvals and documents from the IRB/EC and a regulatory authority, if needed, have been received. Any additional requirements imposed by the IRB/EC or regulatory authority shall be followed, if appropriate.

The Attain Stability Quad Clinical Study was designed to reflect the GCP principles outlined in ISO 14155:2011 and other international clinical requirements outlined below. These include the protection of the rights, safety and well-being of human subjects, controls to ensure the scientific conduct and credibility of the clinical investigation and the definition of responsibilities of the sponsor and investigators. In accordance with ISO 14155:2011, the sponsor shall avoid improper influence on, or inducement of, the subject, monitor, any investigator(s) or other parties participating in, or contributing to, the clinical investigation. All investigators shall avoid improper influence on or inducement of the subject, sponsor, monitor, other investigator(s) or other parties participating in or contributing to the clinical investigation. Adverse Event and Device Deficiency handling in the Attain Stability Quad Clinical Study is ISO 14155:2011 compliant for all participating geographies with the exception that only those AEs which are related to the subject's system, procedure, accessory, or are cardiovascular-related, and all Serious AEs, will be collected. This ensures any AEs which could potentially be relevant will be collected. The scope and duration of the Attain Stability Quad Clinical Study would make collection of all AEs to be a significant burden for investigators and investigative sites. Therefore, only a subset of AEs will be collected in this study, including any that could be potentially relevant.

The principles of the Declaration of Helsinki have been implemented through the IC process, IRB/EC approval, study training, clinical trial registration, pre-clinical testing, risk-benefit assessment and publication policy.

Ultimately, all sites in all geographies will follow and comply with:

- Principles of Declaration of Helsinki
- 21 CFR Part 11 (Electronic Records, Electronic Signatures) (per local law)
- 21 CFR Part 54 (Financial Disclosure by Clinical Investigators)
- The Clinical Trial Agreement
- The procedures described within this CIP
- Local Ethics Board Requirements

In addition to the regulatory requirements outlined above, the study will be conducted according to federal, national and local laws, regulations, standards, and requirements of the countries/geographies where the study is being conducted. These include but are not limited to:

- In the United States, the study will be conducted under an FDA IDE in compliance with 21 CFR Parts:
 - 50: Protection of Human Subjects
 - 56: Institutional Review Boards
 - 812: Investigational Device Exemptions
- In Canada, SOR/98-282, Section 59-88 will be followed and Mandatory Problem Reporting 59(1), 59(2), 60 (1)).
- In EMEA the study will be conducted in compliance with the Active Implantable Medical Device Directive (AIMDD) and Declaration of Helsinki version 2013.
- In Hong Kong and Malaysia, the study will be conducted in compliance with the Declaration of Helsinki version 2013.
- In EMEA, an IB is not required for this study as it is a post market study

The study will be publicly registered prior to first enrollment in accordance with the 2007 Food and Drug Administration Amendments Act FDAAA and Declaration of Helsinki on <http://clinicaltrials.gov> (PL 110-85, section 810(a)). In addition, the study may be registered in local regulatory databases where required by local law.

Approval of the CIP and CIP amendments is required from the following groups prior to any study procedures at a study site:

- Medtronic
- Principal Investigators (where required by local law/regulations)
- Geography-specific regulatory authorities (if regulatory approval is required)
- An independent medical ethics committee or institutional review board.

Similarly, approval of subsequent revisions to the CIP is required at each study site from the above mentioned groups prior to implementation of the revised CIP at the site.

21. Study Administration

21.1. Monitoring

It is the responsibility of Medtronic to ensure proper monitoring of this Attain Stability Quad Clinical Study. Trained Medtronic personnel or delegates appointed by Medtronic may perform study monitoring at the study site in order to ensure that the study is conducted in accordance with the CIP, the CTA, and applicable regulatory and local requirements. Medtronic, or delegates, must therefore be allowed access to the subjects' case histories (clinic and hospital records, and other source data/documentation) upon request as per the Subject IC, Data Protection Authorization (where applicable) and CTA. The principal investigator should also be available during monitoring visits.

Monitoring for the study, including site initiation visits, interim monitoring visits, and closeout visits, will be done in accordance to the study-specific monitoring plan.

Monitoring visits may be conducted periodically to assess site study progress, the investigator's adherence to the CIP, regulatory compliance including but not limited to IRB/EC approval and review of the study, maintenance of records and reports, and review of source documents against subject CRFs. Monitors review site regulatory and study compliance by identifying findings of non-compliance and communicating those findings along with recommendations for preventative/corrective actions to site personnel. Monitors may work with study personnel to determine appropriate corrective action

recommendations and to identify trends within the study or at a particular site. Regulatory documents may be reviewed at each study site.

Frequency of monitoring visits may be based upon subject enrollment, duration of the study, study compliance, number of adverse events, number of deviations, findings from previous monitoring visits and any suspected inconsistency in data that requires investigation.

